3.1.7 Survival Follow-up period

Patients who are permanently discontinued from study treatment for reasons other than death and consent withdrawal for further safety and survival follow-up, regardless of the reason, will enter the survival follow-up period (see Section 5.2.3).

Survival Follow-up (at least every 3 months \pm 14 days from last dose of study drug) will start on the day of the last dose of either study drug and will continue until the study has completed (see Section 3.1.8) or other discontinuation criteria are met (see Section 4.4.4).

All subsequent anticancer therapies should continue to be recorded on the appropriate electronic case report form (eCRF) for the duration of the patient's survival follow up.

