6.3.2.3. Progression-Free Survival (All Substudies)

Progression-Free Survival (PFS) will be calculated as the time from cohort assignment by IWRS until disease progression as assessed by BICR, or death from any cause, whichever comes first. Patients who either have no baseline tumor evaluation or have no post- baseline tumor evaluation will be censored at date of cohort assignment by IWRS. Patients without disease progression will be censored at the date of their last tumor evaluation. Patients who discontinue treatment due to reasons other than disease progression by BICR or death will be censored in the PFS analyses as the date of their last tumor evaluation prior to EOT. Patients who progress or die after missing ≥ 2 consecutive scheduled tumor assessments will be censored at the date of the last tumor evaluation prior to progression or death. Any deaths occurring after end of treatment are not taken into account as a PFS event. Patients who stopped treatment without PD will be censored at their last scan prior to end of treatment. For patients with missing end of treatment visit date, a +7 day window compared to the maximum of last dose date, last on treatment visit date will be applied to create a tentative end of treatment visit date and a cut-off for death occurring after this date. The rules for censoring PFS are summarized in the table below:

Table 5: Censoring scheme for PFS

Situation	Date of progression or censoring	Outcome
No baseline or post-baseline tumor assessments	Randomization / Cohort assignment	Censored
Progression documented between scheduled visits	Date of radiological assessment of measured lesions	Progressed
No progression	Date of last radiological assessment of measured lesions	Censored
Treatment discontinuation for reasons other than disease progression by BICR or death	Date of last radiological assessment of measured lesions	Censored
Death before first PD assessment	Date of death	Progressed
Death between adequate assessment visits	Date of death	Progressed
Death or progression after more than one missed tumor assessment or after end of treatment	Date of last radiological assessment of measured lesions prior to progression or death	Censored

Additional sensitivity analyses will be conducted which consider alternative censoring methods as outlined in FDA guidelines ([FDA 2018](#), [FDA 2015](#)).

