A first sensitivity analysis will consider the same analysis as outlined in Table 5, but also considering clinical progression as an event (either clinical or radiographic progression will be considered as an event, rather than just radiographic).

A second sensitivity analysis will include all post end of treatment assessments, such that subjects who die or progress after end of treatment will be considered as an event, with censoring at the earliest of last scan performed / new anti-cancer treatment. The censoring scheme for this analysis is outlined in Table 6.

Table 6: Censoring scheme for PFS - sensitivity analysis 2

Situation	Date of progression or censoring	Outcome
No baseline or post-baseline tumor assessments	Randomization / Cohort assignment	Censored
Progression documented between scheduled visits	Date of radiological assessment of measured lesions	Progressed
No progression	Date of last scan performed / new anti-cancer treatment	Censored
Death before first PD assessment	Date of death	Progressed
Death between adequate assessment visits	Date of death	Progressed
Death or progression after more than one missed tumor assessment or after end of treatment	Date of death or progression	Progressed

A third sensitivity analysis (Table 7) uses a conservative approach by assigning the date of discontinuation, or missed visit as an event date.

Table 7: Censoring scheme for PFS - sensitivity analysis 3

Situation	Date of progression or censoring	Outcome
No baseline or post-baseline tumor assessments	Randomization / Cohort assignment	Censored
Progression documented between scheduled visits	Date of radiological assessment of measured lesions	Progressed
No progression, treatment ongoing	Date of last radiological assessment of measured lesions	Censored
Treatment discontinuation for reasons other than disease progression by BICR or death	Date of discontinuation	Progressed
Death before first PD assessment	Date of death	Progressed
Death between adequate assessment visits	Date of death	Progressed
Death or progression after more than one missed tumor assessment or after end of treatment	Date of first missed visit	Progressed

PFS will be analyzed using Kaplan-Meier methodology ([Kaplan & Meier 1958](#)). The median duration of PFS will be presented along with the 2-sided 95% CI. If they are calculable, the 25th and 75th percentiles and

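### PFS sensitivity analysis 2 (SAP Table 6) sets the censoring date by what happens later, so its Kaplan-Meier curve is too low and rises with the data cut

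*SAP*

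**What the plan says.** SAP 6.3.2.3 defines a primary PFS analysis (Table 5) and three sensitivity analyses. In the primary analysis, patients who stop treatment without progression are censored at their last scan before end of treatment, and "Any deaths occurring after end of treatment are not taken into account as a PFS event".

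Sensitivity analysis 2 brings post-treatment follow-up back in. Its lead-in reads: "subjects who die or progress after end of treatment will be considered as an event, with censoring at the earliest of last scan performed". It then names the start of a later anti-cancer therapy as the other candidate date. Table 6 gives the rows to be programmed:

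- No progression: dated at "Date of last scan performed / new anti-cancer treatment", outcome censored.
- "Death or progression after more than one missed tumor assessment or after end of treatment": dated at the death or progression itself, outcome progressed.

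New anti-cancer treatment appears only in the first of these rows. The second has no exception for patients who had already started new treatment, and no limit on the time since the last scan.

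The estimator is stated: "PFS will be analyzed using Kaplan-Meier methodology", with estimates at 3, 6, 9 and 12 months.

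**The concern.** Kaplan-Meier needs censoring that does not depend on the later outcome. Under Table 6, whether a patient is censored at month 4 or stays at risk to month 10 is decided by whether that patient dies at month 10. Time after the last scan or after new treatment enters the risk set only for patients who go on to have an event. Each interval after stopping therefore holds too few survivors, and the curve falls too fast. As more of the survivors die, they are moved back into the earlier risk sets, so PFS at a fixed time rises between data cuts although nothing before that time has changed.

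The protocol makes the situation likely. Treatment after study drug is at the investigator's discretion (3.1.5). Scheduled scans are tied largely to time on treatment (Appendix 2), while survival contact continues every 3 months (5.2.3.1). Deaths therefore keep arriving after imaging thins out.

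At stake is the check on Table 5's exclusion of post-treatment events. Analysis 2 is the only planned PFS analysis that counts those events at their own date. As written, it estimates neither PFS regardless of later treatment nor PFS censored at later treatment.

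**Working it through.** The plan gives no figure for this analysis to reproduce. The check applies the Table 6 rows literally.

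**1. Two patients.** Both stop without progression, and both have their last scan and start the same new treatment in month 4. Patient A dies in month 10: at risk to month 10, event. Patient B is alive at the cut: censored at month 4. Up to month 10 their histories are identical.

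**2. Ten patients, by hand.** All have their last scan and start new treatment at month 4. Deaths fall at months 5, 6, …, 14. At each cut, those already dead are events and the rest are censored at month 4.

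| Cut | At risk after month 4 | Table 6 PFS, month 6 | Table 6 PFS, month 8 |
|---|---|---|---|
| Month 8 | 4 | 2/4 = 0.50 | 0/4 = 0.00 |
| Month 11 | 7 | 5/7 = 0.71 | 3/7 = 0.43 |
| All dead | 10 | 8/10 = 0.80 | 6/10 = 0.60 |

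All ten are followed to at least month 8 at every cut, so the correct values are 0.80 and 0.60 each time.

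**3. Simulation with assumed rates (not in the documents).** Exponential times; progression median 4 months; 30% leave without progression; new treatment 1 month later; median survival 9 months from stopping; no scans after stopping.

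The value when every event counts and survivors are followed to the cut can be worked out directly:

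- Progression rate: ln 2/4 = 0.1733 per month.
- Stopping rate: 0.1733 × 0.3/0.7 = 0.0743; total 0.2476.
- Death rate after stopping: ln 2/9 = 0.0770.
- Still on treatment at 12 months: exp(−0.2476 × 12) = 0.0513.
- Off treatment and alive at 12 months: 0.0743/(0.2476 − 0.0770) × [exp(−0.0770 × 12) − 0.0513] = 0.4355 × (0.3969 − 0.0513) = 0.1505.
- Sum: 0.2018, or 20.2%, at any cut from 12 months on.

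Table 6 gives:

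| Follow-up to (months) | 12 | 18 | 24 | 36 |
|---|---|---|---|---|
| 12-month PFS | 8.3% | 13.6% | 16.3% | 18.7% |

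From the earliest to the latest cut, 6-month PFS moves from 35.3% to 39.4% and the median from 4.03 to 4.33 months. With 20% leaving without progression, 12-month PFS runs from 10.0% to 16.5%; with 40%, from 6.1% to 21.2%.

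**4. Second simulation, on the protocol's scan schedule (weeks 9, 18, 27, then every 12 weeks).** Assumed: 12-month uniform accrual; median time to progression 6 months; median time to death 24 months on treatment and 10 months after stopping without progression; 70% of stoppers start new treatment 1 month later. Table 6, 12-month PFS by minimum follow-up:

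| Stop without progression | 12.5 months | 24.5 months | 48.5 months | All events counted |
|---|---|---|---|---|
| 11% | 0.185 | 0.198 | 0.206 | 0.208 |
| 25% | 0.186 | 0.219 | 0.236 | 0.241 |
| 43% | 0.194 | 0.255 | 0.287 | 0.293 |

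The shortfall at the first cut is 0.023, 0.055 and 0.099. With 25% stopping, rules that ignore the later outcome do not drift over these cuts: 0.241 throughout when all events count and survivors are followed to the cut, and 0.181 throughout when everyone is censored at end of treatment without progression.

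**5. Which part of the rule causes it.**

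- Deleting new treatment from the no-progression row leaves the step 3 results unchanged at every cut, because the last scan always comes first.
- Censoring everyone at the last scan before new treatment holds step 3 steady at about 11.7%, but only because every stopper there starts new treatment. If 70% start, 12-month PFS still drifts from 10.5% to 14.7%; in step 4 (25% stopping) it goes 0.179, 0.191, 0.198.

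The last-scan rule for patients without new treatment is therefore part of the defect.

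**The case against.** **The text may censor everyone at new treatment.** The lead-in can be stretched that way. But the same sentence makes post-treatment deaths and progressions events, and the last row of Table 6 has no exception. At best text and table conflict, and step 5 shows that drift remains even on the generous reading.

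**Other analyses count post-treatment events.** This stands. Table 7 (sensitivity analysis 3) also makes them events, dated at the first missed visit, and makes stopping without progression an event. A reader might infer that without analysis 2 nothing in the plan reflects post-treatment events. Table 7 contradicts that; what is particular to analysis 2 is that it keeps each event's own date.

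**The quoted size is near the worst case.** Largely fair. Step 3 assumes no scans after stopping. Yet the analysis is meant to use post-treatment assessments, footnote 13 of the assessment schedule continues imaging until progression, death or loss to follow-up, and Protocol 5.3.3.2.3 asks for every effort to image patients who stop without progression. Appendix 2, however, ties scheduled scans to time on treatment or clinical indication. Later scans would shrink the effect. Twelve months is also the least favourable reported time; the PFS endpoints in Protocol 3.2.2 are the median and 6 months, where the movement is small.

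**No decision rests on it.** Correct. Stage and rejection rules use ORR, and Substudy 4 comparisons are for hypothesis generation only.

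**Conclusion.** The concern holds for sensitivity analysis 2 as written. The censoring date depends on the later outcome, so the Kaplan-Meier estimate lies below the all-events value and rises with the data cut. With 30% stopping without progression and no later scans, 12-month PFS runs from about 8% to 19% against 20%. On the protocol's scan schedule with 11% to 43% stopping, it is about 2 to 10 points too low at 12.5 months' minimum follow-up. In the 30% scenario, 6-month PFS moves about 4 points and the median by 0.3 months. In the second simulation the median stayed at 6.21 months except with 43% stopping at the earliest cut examined (6.01). Direction follows from the rule; size depends on the assumed rates.

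A reader might infer that the trial's PFS result as a whole is unreliable. The documents do not support that. Table 5 censors patients who stop without progression whatever happens later, so it does not share this defect, and ORR does not involve these rules. This is a correction to one sensitivity analysis of a secondary endpoint, worth making because that analysis exists to test Table 5's exclusion of post-treatment events.

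**What to change.** Choose one rule and state it identically in the lead-in and in Table 6.

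**(a) Censor at new treatment.** Add a row: *New anti-cancer treatment started before documented progression or death → last scan on or before its start → Censored, whatever is recorded later.* Add *and before any new anti-cancer treatment* to the last row. Also limit how long after the last scan a death counts. Without that limit, patients who never start new treatment are still handled according to outcome; with it, the estimate stops moving once everyone has been followed through the window.

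**(b) Treatment policy.** Count progression or death regardless of new treatment, and censor event-free patients at a date that does not depend on outcome: last contact known alive without progression, or the data cut. Label the analysis accordingly. Deleting new treatment from the no-progression row is not enough by itself, because survivors would still go back to the last scan.

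**Cost.** A few lines of SAP wording and a small programming change. Under Protocol 3.1.7, "All subsequent anticancer therapies should continue to be recorded"; the section does not mention start dates, so for (a) confirm that the eCRF captures them. Option (a) counts fewer post-treatment events; option (b) assumes no undetected progression once scans stop.

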6.3.2.4. Overall Survival (All Substudies)

Overall Survival (OS) will be calculated from the date of cohort assignment by IWRS until death from any cause. Any patient without a date of death in the database at the time the survival analyses are performed will be censored at the time of their last study contact. Crossover patients (Cohort 4a) will be censored at the time of crossover in the primary analysis of OS.

OS will be analyzed using Kaplan-Meier methodology ([Kaplan & Meier 1958](#)). The median duration of OS will be presented along with the standard error and 2-sided 95% CI. If they are calculable, the 25th and 75th percentiles and the 2-sided 95% CIs around the percentiles will be presented. Kaplan-Meier estimates at 3, 6, 9 and 12 months will also be presented. The Kaplan-Meier survival curves will also be presented. For substudy 4 comparisons between cohorts will be made by considering a hazard ratio, with associated 2-sided 95% confidence interval and p-value, from an unadjusted Cox proportional hazards model.

These analyses will be performed per cohort in substudies 1, 3, 4 and 5 and by dose level in substudy 2. The date of cohort assignment by IWRS, first dose, death, last study contact and OS days will be reported in a by-patient listing.

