3.1.6.1 Eligibility criteria for post-discontinuation study treatment crossover

Patients who permanently discontinue derazantinib due to an AE, withdraw consent, or for any reason other than PD, will not be eligible for crossover.

Patients who meet the following inclusion criteria are eligible for crossover:

1. Documented PD on derazantinib (as confirmed by BICR) as a participant of **Cohort 4a**
2. All ongoing AEs must have resolved to baseline or Common Terminology Criteria for Adverse Events (CTCAE) Grade ≤ 1 (except alopecia and peripheral neuropathy)
3. No new central nervous system (CNS) metastases
4. ECOG PS of 0–2
5. Patient has not received any other systemic anti-cancer therapies after derazantinib administration during the treatment phase.
6. If required, completed palliative radiotherapy (30 Gy or less) ≥ 7 days before the first dose of crossover study treatment.
7. Patient has adequate organ function, as indicated by the laboratory values detailed in Section 4.2.

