OS time will be calculated from the date of cohort assignment by IWRS until death from any cause. Any patient without a date of death in the database at the time the survival analyses are performed will be censored at the time of their last study contact. For patients crossing over from derazantinib to derazantinib-atezolizumab in combination and as an exploratory analysis, HRs for median OS time will be calculated using an IPCW modeling approach ([Rimawi 2012](#)). Overall survival analysis may be repeated upon availability of long-term survival data.

Sensitivity analyses within Substudy 4 will be performed according to the stratification factor composite score and its variables.

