8.3.9 Crossover analysis

In the primary efficacy comparison, patients who crossover to derazantinib-atezolizumab combination are censored at time of crossover. Exploratory safety, PK/ADA, PRO and efficacy analyses will be conducted for the crossover population including all safety events, PK/ADA data, PRO data and RECIST 1.1 responses starting from the date of the first dose of derazantinib-atezolizumab combination.

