As of Protocol Version 5.0, this substudy has been modified. First-line cisplatin-ineligible patients with mUC expressing FGFR1–3 GAs are to be treated with derazantinib 200 mg BID and atezolizumab 1200 mg Q3W in combination, with the co-primary objectives of assessing the safety and efficacy of this regimen in this patient population. If derazantinib 200 mg BID at the SIA is not assessed as safe and tolerable, patients are to be treated with the RP2D determined in Substudy 2. Substudy 3 uses a Fleming's two-stage design. A total sample size of 36 is required to test a null hypothesis of $H_0: \pi \leq 0.25$ versus an alternative hypothesis of $H_a: \pi \geq 0.45$, where π is the true proportion of successes. See Section 6.1.6.3 for details regarding the required sample size and required responses to either accept or reject H_0 .

3.3. Substudy 4

This substudy will enroll FGFR inhibitor-resistant patients with mUC expressing FGFR1–3 GAs. Patients in this substudy are to be randomized (1:1) into two non-comparative groups: Cohort 4a patients will receive derazantinib 300mg QC monotherapy, and Cohort 4b patients will receive derazantinib 300mg QC and atezolizumab 1200 mg Q3W in combination. The primary objective of this substudy is to assess the efficacy

of derazantinib monotherapy and derazantinib-atezolizumab in combination in this patient population. Randomization will be based on a computer-generated randomization schedule via IWRS and will be stratified for key prognostic factors. The presence of visceral metastasis, an ECOG PS of 2, or a preceding FGFR inhibitor treatment interval of less than 6 months (i.e., less than 24 full weeks) will be credited with one point, and patients will be stratified according to their composite score values of 0–1 versus 2–3 points.

Substudy 4 uses a Simon's two-stage design. In Stage 1, 16 evaluable patients will be enrolled for both cohorts. If 1 or fewer patients with an objective response are observed in these 16 patients, the cohort will be stopped. If 2 or more patients with an objective response are observed, an additional 34 patients will be enrolled for a total of 50 patients. The null hypothesis will be rejected if 7 or more responses are seen in these 50 patients.

3.4. Substudy 5

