the 2-sided 95% CIs around the percentiles will be presented. Kaplan-Meier estimates at 3, 6, 9 and 12 months will also be presented. The Kaplan-Meier survival curves will also be presented. For substudy 4 comparison between cohorts will be made by considering a hazard ratio, with associated 2-sided 95% confidence interval and p-value, from an unadjusted Cox proportional hazards model.

The date of cohort assignment by IWRS, first dose, disease progression, death, last tumor assessment and PFS days will be reported in a by-patient listing.

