6.3.3.4. Crossover patients (Substudy 4)

There will be no specific analysis for crossover patients, due to low sample size. Crossover patients will not be included in summary tables/figures and their data will be listed only.

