6.8. Changes to Methods Planned in the Protocol

The planned Inverse Probability of Censoring Weighted (IPCW) modelling approach ([Rimawi 2012](#)) for crossover patients will not be undertaken due to low sample size of crossover patients.

7. Tables, Listings, And Figures

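### Substudy 4 overall survival is censored at an elective crossover in Cohort 4a only, with no all-deaths analysis, an ambiguous rule for crossover patients and a cohort comparison that ignores the randomisation stratum

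*SAP*

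**What the plan says.** SAP 6.3.2.4 defines OS from cohort assignment to death and adds: "Crossover patients (Cohort 4a) will be censored at the time of crossover in the primary analysis of OS". All other patients without a death date are censored at last contact. The Substudy 4 comparison is a hazard ratio with confidence interval and p-value.

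Under Protocol 3.1.6 and 3.1.6.1, crossover is optional, at the investigator's discretion with sponsor and patient agreement. It needs progression confirmed by central review, recovered adverse events, no new CNS metastases and ECOG 0–2. A further criterion reads "Patient has adequate organ function, as indicated by the laboratory values detailed in Section 4.2".

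The protocol is not uniform. Section 8.3.9 says "In the primary efficacy comparison, patients who crossover to derazantinib-atezolizumab combination are censored at time of crossover". Section 8.3.4.2 states crossover censoring for DOR and PFS, but its OS paragraph reads "OS time will be calculated from the date of cohort assignment by IWRS until death from any cause" and offers an exploratory inverse-probability-of-censoring-weighted (IPCW) analysis. SAP 6.8 withdraws that analysis: it "for crossover patients will not be undertaken due to low sample size of crossover patients".

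SAP 6.3.3.4 states: "Crossover patients will not be included in summary tables/figures and their data will be listed only".

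On randomisation, SAP 3.3 says "patients will be stratified according to their composite score values of 0–1 versus 2–3 points". The cohort comparisons of OS, PFS and DOR nevertheless come "from an unadjusted Cox proportional hazards model". SAP 6.3.3.2 adds separate analyses within each composite-score level.

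**The concern.** There are three linked points.

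1. **Informative, one-sided censoring.** Patients are censored at a moment defined by progression, which raises the hazard of death, and by fitness, which selects the better-prognosis progressors. The two pull in opposite directions. Only Cohort 4a is affected. Other later anticancer therapy is recorded (Protocol 3.1.7) but does not censor OS. PFS has three sensitivity analyses and OS has none. Survival follow-up continues after treatment stops (Protocol 4.5.2), so deaths after crossover are collected but enter no OS estimate. The 4a Kaplan-Meier median and landmark estimates are affected as well as the hazard ratio.
2. **Ambiguous membership.** Read literally, 6.3.3.4 removes crossover patients from the OS tables, whereas 6.3.2.4 keeps them until crossover. The two readings give different results.
3. **Stratum ignored.** An unadjusted Cox model after stratified randomisation on prognostic factors pulls the hazard ratio towards 1 and loses some power. It does not inflate type I error.

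At stake is the reliability of the OS signal that Substudy 4 would pass to a future comparative study.

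**Working it through.** **The plan's own figures.** The documents give no OS hypothesis, event count or power. The only design figures for Substudy 4 concern ORR (16 then 50 per cohort, stop at ≤1, reject at ≥7). Type I error and power are the sum over x = 2 to 16 of b(16, x, p) × P(Bin(34, p) ≥ 7 − x). This gives 0.0448 at p = 0.07 and 0.8027 at p = 0.20, as stated, and the OS issue does not touch them.

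**Crossover simulation.** All survival inputs are assumptions, not taken from the documents: median 3 months to first event, 85% of first events progressions, equal true OS in both cohorts, no effect of crossover on survival, follow-up 6 to 24 months, 200,000 patients per cohort. The true HR (4b/4a) is 1.00. The columns give the share of 4a progressors who cross.

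| Who crosses (post-progression median) | Rule | 10% | 20% | 40% |
|---|---|---|---|---|
| Random (4 months) | censored at crossover | 1.03 | 1.06 | 1.16 |
| Fitter half only (6 v 2.7 months) | censored at crossover | 1.00 | 1.00 | 1.00 |
| Fitter half only (8 v 2 months) | censored at crossover | 0.99 | 0.97 | 0.92 |
| Random | crossovers excluded | 0.99 | 0.97 | 0.93 |
| Fitter half (6 v 2.7) | crossovers excluded | 0.96 | 0.91 | 0.79 |
| Fitter half (8 v 2) | crossovers excluded | 0.94 | 0.88 | 0.71 |
| Any | all deaths counted | 1.00 | 1.00 | 1.00 |

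A repeat under the same assumptions reproduced the censored rows to within about 0.01. Its exclusion figures at 40% were somewhat milder (0.97, 0.83, 0.75) but in the same direction. At 40%, the 4a median OS reads 7.2 to 8.5 months when censored, against about 7.5 with all deaths counted.

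**A second set of assumptions** (median 3 months to progression, 24 months to death without progression, about 6 months after progression with a 3-fold fit/unfit hazard gap, 24 months of follow-up; 10/25/50% of progressors crossing):

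- Censored: 1.01/1.05/1.12 if random; 0.97/0.93/0.80 if the fitter cross.
- Excluded: 0.98/0.96/0.88 and 0.94/0.85/0.59.
- All deaths counted: 0.996 to 1.002.
- Censoring drops 7% to 40% of 4a deaths.

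**Against sampling error.** With 50 per cohort and about 70 deaths, the SE of log HR is about 2/√70 = 0.24. At 10% crossing, ln(1.03) = 0.03, about one-eighth of an SE. At 40%, ln(1.16) = 0.15, about 0.6 of an SE.

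**Stratification.** 8,000 simulated trials of 50 + 50, two equal strata, exponential survival, follow-up 6 to 24 months, two-sided 5% test. Power, mean HR and SE are at a true HR of 0.6 (about 63 deaths). Each cell is unadjusted v stratified.

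| Stratum HR | Power | Mean HR | SE | Rejection under the null |
|---|---|---|---|---|
| 1.5 | 0.50 v 0.51 | 0.60 v 0.60 | 0.259 v 0.261 | 0.043 v 0.043 |
| 2 | 0.47 v 0.51 | 0.61 v 0.60 | 0.258 v 0.262 | 0.041 v 0.053 |
| 3 | 0.40 v 0.50 | 0.64 v 0.60 | 0.258 v 0.263 | 0.028 v 0.048 |

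**The case against.** The censoring is deliberate. Protocol 8.3.9 supports it in general terms, and the IPCW analysis in the protocol's OS paragraph presupposes it. Only 4a patients can cross, so a one-cohort rule follows from the design. It targets survival without the added combination, and an all-deaths analysis answers a different question. No bias is shown for this trial: the inputs are assumed, and one scenario gives no shift under censoring. The SAP calls the crossover sample low, whereas the 40% scenario would mean about 0.40 × 0.85 × 50 = 17 crossovers in a full cohort. At 10% (about 4 patients) the shift is trivial. SAP 6.3.3.4 sits under exploratory analyses, probably concerns crossover-phase data only, and the exclusion reading would contradict the mITT definition. The cohorts are called non-comparative, and the stratum is covered by subgroup analyses.

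Much of this stands as a limit on size. It does not close the gaps. Survival without crossover is a legitimate target, but simple censoring estimates it only if crossover is unrelated to prognosis, and the weighting meant to address that has been dropped. Low crossover numbers make an all-deaths analysis easier to interpret; they are no reason to omit it. The intended meaning of 6.3.3.4 is likely but unstated. Within-stratum analyses do not supply a pooled stratified estimate, and an HR with p-value will be reported regardless of the label.

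**Conclusion.** The concern holds and is minor. No specified OS analysis counts deaths after crossover, the censoring is plausibly informative and confined to 4a, and 6.3.3.4 needs reconciling with 6.3.2.4. Across both sets of assumptions, with a true HR of 1, censoring gives 0.97 to 1.03 when 10% of progressors cross and 0.80 to 1.16 over the full range examined (up to 50%). The sign depends on who crosses, so it cannot be corrected by judgement afterwards. Excluding crossovers gives an HR below 1, favouring 4b, in every scenario tabulated. Counting all deaths returns about 1.00. Leaving out the stratum costs about 1, 4 and 10 points of power at stratum HRs of 1.5, 2 and 3.

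These sizes rest on assumed survival and crossover rates; the SAP gives no crossover count. The ORR decision rules are unaffected. If crossovers are as few as the SAP suggests, the actual shift is small against an SE of about 0.24.

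**What to change.** - In SAP 6.3.2.4, report for Substudy 4 OS from assignment to death regardless of crossover, alongside the crossover-censored OS. State the number of crossovers and what each analysis estimates.
- In SAP 6.3.3.4, say which data are listed only, for example data from the crossover phase, and that crossover patients otherwise stay in the main efficacy outputs.
- Stratify the Substudy 4 Cox models for OS and PFS by the composite score (0–1 v 2–3), keeping the planned subgroup analyses. For DOR this is optional: ORRs of 7% to 20% in 50 patients give only about 4 to 10 responders per cohort. The Fisher tests can stay.

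The cost is SAP wording, one extra output and a STRATA statement; no new data are needed. There are two downsides. The all-deaths analysis compares monotherapy with optional later combination against combination from the start. The stratified SE is about 1% to 2% larger (0.261 to 0.263 v 0.258 to 0.259).
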